**Table 22: Stopping Boundaries for Toxicity and Futility Monitoring in Each of Cohorts A-D**

	Toxicity Stopping Boundaries		Futility Early Stopping Boundaries	
Number of Subjects (inclusive)	Num DLTs (inclusive) are considered too toxic	Actions for toxicity monitoring	Num. Responses (inclusive) are considered futile	Actions for futility monitoring
10	4 - 10	Early stopping	0 - 1	Early stopping
15	5 - 15	Early stopping	0 - 2	Early stopping
20	6 - 20	Early stopping	0 - 4	Early stopping
26	8 - 26	Reach to Nmax	0 - 6	Reach to Nmax

### 9.3.1. IND Office Futility and Safety Monitoring

Safety oversight will be performed by the SRC, the meeting minutes will be submitted to the IND Office Medical Affairs & Safety group upon availability.

**Table 23: Operating Characteristics for Futility Monitoring in each of Cohorts A-D**

True Response Rate	Early stop probability for futility	Average sample size
0.1	0.9633	12.29
0.2	0.6713	17.72
0.3	0.2906	22.57
0.4	0.0811	25.00
0.5	0.0153	25.79
0.6	0.002	25.97

**Table 24: Operating Characteristics for Toxicity Monitoring in each of Cohorts A-D**

True DLT rate	Probability of Early Stop for toxicity	Average Sample size
0.1	0.0235	25.70
0.2	0.2509	22.92
0.3	0.636	17.84
0.4	0.8954	13.53
0.5	0.9834	11.22

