## 3.3. Phase 2 Design

Enrollment in Phase 2 will start once the RP2D has been determined in Phase 1. This Phase 2 study will have four cohorts:

- Cohort A: DS-1594b monotherapy for R/R AML with MLL-r,
- Cohort B: DS-1594b monotherapy for R/R AML with NPM1m,
- Cohort C: DS-1594b in combination with azacitidine and venetoclax for R/R AML with NPM1m or MLLr
- Cohort D: DS-1594b in combination of mini-HCVD for R/R ALL with MLLr

Subjects enrolled in Cohorts A and B will receive the RP2D dose of DS-1594b determined in Phase 1. Cohorts C and D will enroll an initial 6 subjects in a safety run-in at one dose level below the RP2D (Dose level 0) with DS-1594b dose titration as specified below.

Cohorts A and B (single agent cohorts) will enroll a maximum of 26 subjects, and Cohorts C and D (combination cohorts) will enroll a maximum of 32 subjects, to allow reasonable determination of CRc within 3 months of therapy initiation.

For the combination cohorts (C & D) there will be a safety-run in evaluation with pre-defined toxicity stopping rules to be implemented for early DLT evaluation as per following plan:

- Safety run-in evaluation by the Safety Review Committee of the first 6 subjects in cohorts C and D will occur after 6 subjects have completed at least one cycle of treatment (or at least 28 days from the first day of treatment).
- Enrollment will be paused while the first 6 subjects are evaluated for safety. Each combination cohort will be evaluated independently.
  - If  $\leq 1$  of the 6 subjects experiences DLT in the first cycle of treatment, the treatment combination will be considered as safe and the DS-1594b dose can be escalated to the RP2D (Dose level 1) for the treatment of the next 6 patients (repeat the safety run-in evaluation). If the RP2D (Dose level 1) is considered safe, continue enrollment of an additional 20 subjects at the RP2D (i.e. total subjects treated at the RP2D will be 26 subjects; total cohort size will be 32 subjects). If  $\geq 2$  of 6 subjects at the RP2D experiences DLT in the first cycle of treatment, de-escalate and continue enrollment of an additional 20 subjects at Dose Level 0.

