  - If  $\geq 2$  of 6 subjects have DLTs in the first cycle of treatment at Dose Level 0, then an additional 6 subjects will enroll at a next lower dose level to be determined by the Principal Investigator and Safety Review Committee after reviewing the safety, efficacy, and PD data from the first 6 subjects enrolled ([Table 6](#)[Table 6](#), [Table 7](#)[Table 7](#)). If  $\leq 1$  of the additional 6 subjects treated at the lower dose level experience DLTs, this treatment combination will be considered as safe and continue to enroll to a total of 26 subjects (i.e. an additional 20 subjects at the lower dose level; total cohort enrollment of 32 subjects). If  $\geq 2$  of these 6 additional subjects experienced DLTs, then enrollment at the current dose level will be closed.
- Subjects must receive at least 75% of the doses of DS-1594b, azacitidine (Phase 2 only), venetoclax (Phase 2 only), or miniHCVD (Phase 2) during the first 28 days on trial (i.e. during Cycle 1) to be considered evaluable during the DLT evaluation period. Any subjects who are not evaluable for DLT in either cohort during the safety-run in period will be replaced for the assessment of DLT rate. This will allow for early identification of significant toxicities and early stoppage in the combination cohorts.
- The Safety Review Committee (SRC) will meet when there are enough DLT-evaluable subjects to review in each cohort who have completed the DLT evaluation period. The SRC will review the DLT data, other AE data, and available PK/PD, ECG, and laboratory data before proceeding to expansion of each of the cohorts to enroll the additional 20 subjects.

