### **9.3. Futility and Toxicity Monitoring**

The historical data suggest a response rate of 25% in subjects with R/R AML or R/R ALL with NPM1m or MLLr using a variety of different therapies, and the target response rate is

40% with acceptable safety. The response rate is defined as CR + CRh rate within 3 months of therapy initiation in cohorts A, B and C and CR/CRi rate within 3 months of therapy initiation in Cohort D. The cohort will be stopped early if the data suggest that:

$$\Pr(P_E \leq 0.40 | \text{data}) > 0.95, \text{ or}$$

$$\Pr(P_T > 0.2 | \text{data}) > 0.85.$$

where  $P_E$  is the response rate and  $P_T$  is the probability of DLT for experimental treatments, respectively. We assume  $P_E$  and  $P_T$  follow a priori  $\sim \text{beta}(0.5, 0.5)$ . That is, if at any time during the study we determine that there is more than 95% chance that the response rate would be at less than 40%, the cohort will be stopped due to futility. Or if at any time during the study, we determine that there is more than 85% chance that the toxicity rate is more than 20%, the cohort will be stopped due to toxicity. DLT observations from IPDE will not be used in toxicity monitoring.

The futility and toxicity monitoring will be conducted separately for each of four cohorts, starting once the 10th subject in a cohort has been evaluated, and thereafter in groups of 5 subjects, except the last group. The design parameters are set the same for cohorts A-D, each with a maximum of 26 subjects per cohort, excluding the safety run-in period for the first 6 subjects in each of Cohorts C and D (Section 3.3).

The stopping boundaries for futility and toxicity based on these assumptions and monitoring conditions are provided in [Table 22](#)[Table 22](#). The operating characteristics are summarized in [Table 23](#)[Table 23](#) and in [Table 24](#)[Table 24](#) for futility and toxicity monitoring, respectively. [Table 25](#)[Table 25](#) presents the overall early stopping probabilities for futility and toxicity monitoring. Bayesian Toxicity Monitoring software and Bayesian Efficacy monitoring with Posterior Probability software on <https://trialdesign.org> were used for the design of toxicity and futility monitoring.

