**Table 25: Overall early stopping probabilities for Futility and Toxicity Monitoring in each of Cohorts A-D**

True DLT rate	True Response Rate	Overall probability of early stop
0.1	0.2	0.6790
0.1	0.4	0.1027
0.1	0.6	0.0255
0.2	0.2	0.7538
0.2	0.4	0.3117
0.2	0.6	0.2524
0.4	0.2	0.9656
0.4	0.4	0.9039
0.4	0.6	0.8956

**Table 26** [Table 26](#) presents the estimation precision (e.g., 95% credible intervals) under various scenarios with different numbers of observed responses, given that a cohort is not stopped early and 26 subjects have been enrolled. For example:

- if 11 of the 26 subjects achieve the response (CR + CRh for Cohorts A-C and CR+Cri for Cohort D), the 95% credible interval of the response rate will be (25%, 61.3%).
- if 8 of the 26 subjects achieve the response, the 95% credible interval of the response rate will be (15.8%, 49.8%).

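### Tables 24 and 25 are titled for all four cohorts but hold only for Cohorts A and B: they omit the second six-subject run-in that lies inside the 26 in Cohorts C and D

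*Combined protocol and SAP*

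**What the plan says.** Section 9.3 sets one Bayesian rule for all four cohorts. On toxicity, if at any time "we determine that there is more than 85% chance that the toxicity rate is more than 20%, the cohort will be stopped due to toxicity". Monitoring runs "starting once the 10th subject in a cohort has been evaluated, and thereafter in groups of 5 subjects, except the last group". The parameters are common to the cohorts, with a "maximum of 26 subjects per cohort, excluding the safety run-in period for the first 6 subjects in each of Cohorts C and D". Table 22 gives the DLT boundaries as 4 of 10, 5 of 15 and 6 of 20, with 8 of 26 at the maximum.

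Table 24, which gives the toxicity-stopping probabilities, is titled "Operating Characteristics for Toxicity Monitoring in each of Cohorts A-D". Table 25 is titled "Overall early stopping probabilities for Futility and Toxicity Monitoring in each of Cohorts A-D".

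Section 3.3 gives Cohorts C and D a sequence that A and B do not have:

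- Six subjects start at Dose Level 0. With at most one DLT, the next six are treated at the RP2D and the run-in evaluation is repeated.
- If those six also pass, 20 more follow at the RP2D, which makes 26 there and 32 in the cohort.
- If two or more "of 6 subjects at the RP2D experiences DLT in the first cycle of treatment, de-escalate and continue enrollment" with 20 further subjects at Dose Level 0.
- If Dose Level 0 fails first, six subjects go to a lower level. If two or more "of these 6 additional subjects experienced DLTs, then enrollment at the current dose level will be closed".

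**The concern.** The declared exclusion accounts for 32 − 6 = 26, that is, for the first run-in only. The second run-in six are part of the 26, and they face a rule at n = 6 that neither table contains. So two of the four cohorts are given operating characteristics of a design they do not follow.

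Section 3.3.1 presents the run-in and the Section 9.3 monitoring together as the safeguards for the first use of DS-1594b in combination. Their joint behaviour is given nowhere. A reader of Section 9.3 cannot see how often a combination cohort would finish at the RP2D, at a lower level, or not at all.

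**Working it through.** **Inputs.** Beta(0.5, 0.5) prior, 0.85 cutoff, looks at 10, 15 and 20, maximum 26 (Section 9.3); boundaries (Table 22); gate of two or more DLTs in 6 (Section 3.3). The documents give no DLT rates for Dose Levels −1, 0 and 1, so equal rates are assumed unless stated.

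**Step 1: the plan's own figures.** The posterior rule returns the Table 22 boundaries. An exact binomial recursion with stops at ≥4/10, ≥5/15 and ≥6/20, and no look at 6, gives 0.0235, 0.2509, 0.6360, 0.8954 and 0.9834 at DLT rates 0.1 to 0.5. Average N is 25.70, 22.92, 17.84, 13.53 and 11.22. This is Table 24 exactly. Combining with futility as 1 − (1 − P_tox)(1 − P_fut) returns Table 25 within 0.0001. The tables contain no gate.

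**Step 2: the gate.** g = P(X ≥ 2 of 6) = 1 − (1 − p)^6 − 6p(1 − p)^5. At p = 0.2: 1 − 0.2621 − 0.3932 = 0.3446 (from unrounded terms).

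**Step 3: a Table 22 stop after a passed gate.** Call this c. It is the same recursion, started at n = 6 with 0 or 1 DLT. At p = 0.2, c = 0.1145.

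**Step 4: a dose level does not complete its 26.** g + (1 − g)c. At p = 0.2: 0.3446 + 0.6554 × 0.1145 ≈ 0.420.

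**Step 5: the cohort stops, over the whole Section 3.3 path.** Failing at the RP2D leads to Dose Level 0 and is not a stop. Only failure at Dose Level 0 and then at the lower level, or a later Table 22 stop, ends the cohort. With equal rates, and Table 22 counted on the 26 at the final dose level, this is g² + (1 − g²)c. At p = 0.2: 0.1188 + 0.8812 × 0.1145 ≈ 0.220.

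**Step 6: 26 completed at the RP2D.** (1 − g)²(1 − c). At p = 0.2: 0.4295 × 0.8855 ≈ 0.380.

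| True DLT rate | 0.1 | 0.2 | 0.3 | 0.4 | 0.5 |
|---|---|---|---|---|---|
| Table 24 | 0.0235 | 0.2509 | 0.636 | 0.8954 | 0.9834 |
| Gate failure, g | 0.1143 | 0.3446 | 0.5798 | 0.7667 | 0.8906 |
| Dose level does not complete 26 | 0.1209 | 0.4197 | 0.7437 | 0.9302 | 0.9893 |
| Average N at that level | 23.65 | 18.39 | 12.80 | 8.95 | 7.05 |
| Table 22 stop given gate passed, c | 0.0074 | 0.1145 | 0.3901 | 0.7010 | 0.9018 |
| Cohort stops, whole path | 0.0204 | 0.2196 | 0.5951 | 0.8768 | 0.9797 |
| Completes 26 at the RP2D | 0.7787 | 0.3803 | 0.1077 | 0.0163 | 0.0012 |

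**Step 7: Table 25, dose-level reading.** At DLT 0.2 and response 0.4: 1 − (1 − 0.4197)(1 − 0.0811) ≈ 0.467, against 0.3117 stated. At DLT 0.1 and response 0.6: 0.123 against 0.0255. These are chances of not completing a dose level, not of stopping the cohort.

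**Step 8: sensitivity.**

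- *Which subjects are counted.* Suppose the Bayesian count covers subjects 7 to 32 whatever their dose. A failed RP2D gate then leaves the count running, and the cohort-stop probability at p = 0.2 is 0.6554 × 0.2509 + 0.3446 × 0.4197 ≈ 0.31.
- *DLT rates that fall with dose.* With 0.05, 0.10 and 0.20 at Dose Levels −1, 0 and the RP2D, the whole-path stop probability is 0.07 and 0.51 complete at the RP2D. With 0.10, 0.15 and 0.20, the figures are 0.10 and 0.45.

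**The case against.** The best defence is that Tables 24 and 25 describe the Bayesian rule alone and do so correctly. Section 9.3 names that rule and points to Section 3.3 for the run-in, and Section 3.3 discloses the gates in full. On the event that Table 24 names, an early stop of the cohort, the whole-path figures differ from it by at most about 4 points (0.636 against 0.595) and are slightly lower at every rate.

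Much of this stands. The printed arithmetic is right, and the fault is one of scope. What fails is the exclusion: it names the first 6 subjects only, and leaving out the second six as well would give 20, not 26.

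A reader might also infer three stronger things that the documents do not support.

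- *That a combination at the 20% rate has a 42% chance of a toxicity stop against the 25% stated.* The 42% is the chance of not completing one dose level. Failing the gate at the RP2D de-escalates and enrolment continues.
- *That the later looks protect less than stated.* The 0.0074 to 0.9018 row is conditional on at most one DLT in six, after the early-toxic courses have been removed. Table 24 is unconditional. A lower conditional figure follows from adding a gate and is not lost protection.
- *That corrected figures must look less favourable.* The sign changes with the event and with the subjects counted.

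**Conclusion.** The point holds as one of scope. Tables 24 and 25 are right for Cohorts A and B. None of the readings examined for Cohorts C and D returns Table 24: at a 20% DLT rate they give 0.420 (dose level not completed), 0.1145 (Table 22 stop after a passed gate), 0.220 (cohort stop, counted by dose level) and about 0.31 (cohort stop, counted over subjects 7 to 32), against 0.251.

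The dose-level and conditional figures rest only on the stated rules and the binomial model. The whole-path figures also assume equal DLT rates at all levels, and rates that fall with dose bring the stop probability well below Table 24. The plan does not say which subjects the Bayesian count covers after a de-escalation. Read literally, excluding the first 6 would drop the very subjects treated first at Dose Level 0. The error should be corrected, but it does not undermine the monitoring rules themselves.

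**What to change.** Limit the titles of Tables 24 and 25 to Cohorts A and B. Add a table for Cohorts C and D, computed with the Section 3.3 gates and the Table 22 looks together. For each scenario it should:

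- report separately the probability of completing at the RP2D, at Dose Level 0 and at the lower level, and of stopping or closing, with the average N;
- state the DLT rate assumed at each dose level, with a sensitivity range;
- state which subjects the Bayesian count covers after a de-escalation.

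The cost is a short exact calculation, two retitled tables and one new one. No boundary, dose, sample size or conduct rule changes.

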**Table 25: Overall early stopping probabilities for Futility and Toxicity Monitoring in each of Cohorts A-D**

True DLT rate	True Response Rate	Overall probability of early stop
0.1	0.2	0.6790
0.1	0.4	0.1027
0.1	0.6	0.0255
0.2	0.2	0.7538
0.2	0.4	0.3117
0.2	0.6	0.2524
0.4	0.2	0.9656
0.4	0.4	0.9039
0.4	0.6	0.8956

**Table 26** [Table 26](#) presents the estimation precision (e.g., 95% credible intervals) under various scenarios with different numbers of observed responses, given that a cohort is not stopped early and 26 subjects have been enrolled. For example:

- if 11 of the 26 subjects achieve the response (CR + CRh for Cohorts A-C and CR+Cri for Cohort D), the 95% credible interval of the response rate will be (25%, 61.3%).
- if 8 of the 26 subjects achieve the response, the 95% credible interval of the response rate will be (15.8%, 49.8%).

**Table 26: 95% Credible Intervals Under Various Scenarios with Different Numbers of Responses**

Number of responses	Empirical response rate	95% Credible interval
6	23.1%	(10.3%, 41.5%)
8	30.8%	(15.8%, 49.8%)
10	38.5%	(21.8%, 57.6%)
11	42.3%	(25.0%, 61.3%)
12	46.2%	(28.2%, 64.9%)
14	53.8%	(35.1%, 71.8%)
16	61.5%	(42.4%, 78.2%)
18	69.2%	(50.2%, 84.2%)

## 9.4. Statistical Analysis Plan

### 9.4.1. Analysis Sets

#### 9.4.1.1. Efficacy Analysis Set

The efficacy analysis set is all subjects with MLLr or NPM1m who received at least one dose of DS-1594b. Each cohort will be analyzed separately for efficacy.

#### 9.4.1.2. Safety Analysis Set

Safety analysis set is all subjects who received at least one dose of DS-1594b.

#### 9.4.1.3. DLT Evaluatable Set

The DLT Evaluatable Set will include all subjects in the Safety Analysis Set from Dose Escalation who experienced a DLT during the DLT evaluation period (first 28-day cycle), or who has not had a DLT and has received at least 42 out of the 56 DS-1594b doses and has completed the DLT evaluation period.

Formatted: C-Hyperlink

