Formatted: C-Hyperlink

- if the observed DLT rate at the current dose is 0.157 or less, escalate the dose to the next higher dose level;
- if the observed DLT rate at the current dose is more than 0.238, de-escalate the dose to the next lower dose level;
- otherwise, stay at the current dose.

Evaluation by the abovementioned BOIN rule will be done for each dose level separately based on the cumulative number of DLT evaluable subjects treated in that dose level and regimen (i.e., QD or BID). In case the multiple dosing regimens are initiated simultaneously and parallel enrollment is allowed in the multiple dosing regimens, the evaluation by the BOIN rule for each dose level and regimen would be made separately. DLT observed after intra-patient dose escalation (IPDE) will not be considered in the dose escalation/de-escalation decision (See Section 6.9 for details about IPDE). For the purpose of overdose control, doses  $j$  and higher levels will be eliminated from further examination if  $\Pr(p_j > 0.2 | \text{data}) > 0.95$  and at least 3 subjects have been treated at dose level  $j$ , where  $p_j$  is the true DLT rate of dose level  $j$ ,  $j = 1, \dots, 6$ . This posterior probability is evaluated based on the beta-binomial model  $y_j | p_j \sim \text{binomial}(p_j)$  with  $p_j \sim \text{uniform}(0,1)$ , where  $y_j$  is the number of subjects who experienced DLT at dose level  $j$ . When the lowest dose is eliminated, stop the trial for safety. The probability cutoff 0.95 is chosen to be consistent with the common practice that when the target DLT rate  $\leq 1/6$ , a dose with 2/3 subjects experienced DLT is eliminated. The above dose escalation/de-escalation and elimination rule can be equivalently presented in [Table 4](#), which will be used to conduct the trial.

Formatted: C-Hyperlink

The steps to implement the BOIN design are described as follows:

1. Three subjects in the first cohort are treated at dose level 1 (70 mg twice daily). Each cohort will include a minimum of 3 subjects.
2. To assign a dose to the next cohort of subjects, conduct dose escalation/de-escalation according to the rule displayed in [Table 4](#). When using [Table 4](#), please note the following:
  - a. “Eliminate” means eliminate the current and higher doses from the trial to prevent treating any future subjects at these doses because they are overly toxic.

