  - Grade 3 or 4 Differentiation Syndrome which improves to  $\leq$  Grade 1 within 7 days of the start date of  $\geq$  Grade 3 Differentiation Syndrome and which is not associated with end-organ damage. Note: Grade 1 is mild, Grade 2 is moderate, Grade 3 is serious, and Grade 4 is life-threatening.

- CTCAE Grade 3 QTcF prolongation (based on the average of 3 triplicate 12-lead readings or Holter monitor reading)
- Results in dose-reduction or discontinuation of therapy
- Any treatment-related death;
- Subjects not considered evaluable due to insufficient dosing (at least 75% of doses of study drugs) and who do not develop a toxicity that is considered a DLT will be replaced. These subjects may continue therapy on trial after discussion with the Principal Investigator if they are having clinical benefit and the reasons for continuation and potential benefit/risk profile for the subject must be clearly documented in the medical records.
- **Phase 2 only:** For subjects in venetoclax- or Mini-HCVD-containing regimens (cohorts C and D) who do not receive venetoclax or Mini-HCVD on Day 1 due to logistical and/or financial reasons, the DLT period will be extended to 28 days from the first dose of venetoclax or Mini-HCVD. For evaluation of hematologic-related DLT, the DLT evaluation period will be 42 days from the first dose of venetoclax or Mini-HCVD.
- Subjects must receive at least 75% of the doses of DS-1594b, azacitidine (Phase 2 only), venetoclax (Phase 2 only), or miniHCVD (Phase 2) during the first 28 days on trial (i.e. during Cycle 1) to be considered evaluable during the DLT evaluation period. Subjects who receive less than these planned number of doses of each drug during the first 28 days on trial will not be considered evaluable during the DLT evaluation period. However, if such subjects develop a toxicity that would normally be considered a DLT this will still be captured as a DLT. Any toxicity that meets the criteria for DLT during the first 28 days of trial in a subject who has received at least one dose of trial medication will constitute a DLT.
- For subjects who discontinue therapy, the reason for treatment discontinuation will be documented.
- Dose modifications other than the ones mentioned above can be considered after discussion with the PI and proper documentation of the rationale.

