## 5. TREATMENT PLAN

### 5.1. Phase 1 Dose Administration

#### 5.1.1. Study Treatment

The orally administered film-coated tablet formulation of DS-1594b will be supplied by Daiichi Sankyo and are in 20 mg, 50 mg, and 200 mg dose strengths.

The first dose cohort will start at 70 mg twice daily, approximately every 12 hours. For provisional dose levels beyond the first dose cohort, see [Figure 1](#)[Figure 1](#). Alternative doses or dosing regimens may be enrolled based on emerging clinical data, including intermediate dose levels or dose de-escalation. BID and QD cohorts can be enrolled in parallel and will be evaluated independently for DLT.

Formatted: C-Hyperlink

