#### 5.1.2. Dose Administration Guidance

DS-1594b will be administered orally on a continuous twice daily (or once daily) regimen. In this study a complete cycle of treatment is defined as 28 days. The Investigator must instruct the subject to take the study drug (DS-1594b) exactly as prescribed:

1. For BID dosing, subjects should take DS-1594b tablets twice daily at approximately the same time each day for morning and evening doses; for QD dosing, subjects should take DS-1594b tablets once daily at approximately the same time each day for morning doses.
2. Each dose of DS-1594b is to be taken with a glass of water (at least 8 ounces – approximately 250 mL) and consumed over as short a time as possible (i.e., not slower than 1 tablet every 2 minutes).
3. Subjects should be instructed to swallow the tablets whole and not to chew them.
4. DS-1594b should be administered under fasting condition, at least 1 hour before or 2 hours after a meal.
5. For BID dosing, the morning and evening doses should be taken 12 ( $\pm$  4) hours apart, although 12-hour interval is recommended. If a dose is not taken within 4 hours of the planned dosing time, the missed dose should not be replaced. On days when serial PK

blood samples are to be collected especially those with 12 hours post-dose timepoint (see Section 8.4.1), subjects should keep the 12-hour interval between morning and evening doses.

6. On days when PK blood samples are to be collected, subjects will be instructed to hold their dose until arrival at the study center; the site will remind subjects one day before not to take the morning dose at home. DS-1594b will be administered at the site in the morning after the pre-dose ECG assessment and PK blood draw and prior to the post-dose PK blood draws. The exact date/time of drug administration should be recorded in the eCRF. If a subject vomits within the first 4 hours post-treatment on a full PK sampling day, the exact time of vomiting should be recorded on the eCRF.
7. All pre-dose PK samples should be drawn just before DS-1594b dosing. The sampling time of the pre-dose PK sample and the dosing time of DS-1594b must be precisely recorded in the eCRF. Furthermore, the dosing time of DS-1594b on the previous day must be precisely recorded in the eCRF.

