### **9.1. Phase 1**

The primary objective of Phase 1 is to determine the MTD and RP2D of DS-1594b when administered as a single agent in subjects with R/R AML or R/R ALL, including subjects with or without MLLr or NPM1m using a Bayesian optimal interval (BOIN) design (Liu and Yuan, 2015; Yuan et al., 2016) to find the MTD. The details of the BOIN design to be used in the Phase 1 are outlined in Section 3.2.

According to the BOIN design, cohorts of 3 subjects will be treated at each dose level. If a dose level is found to be safe by the BOIN design we will escalate to the next higher dose level. Evaluation for above mentioned BOIN rule will be done for each dose level and dosing regimen (i.e., QD vs BID) separately based on the cumulative number of DLT evaluable subjects treated in that dose level. In case the multiple dosing regimens are initiated simultaneously and parallel enrollment is allowed in the multiple dosing regimens, the evaluation for BOIN rule for each dose level and dosing regimen would be made separately. Up to 9 additional subjects may be enrolled at each dose level that has already been deemed to be safe with the intent to gain additional information on safety and efficacy at different dose levels, to guide selection of optimal biologically effective RP2D. Although all R/R ALL and R/R AML subjects, irrespective of mutations, will be allowed during the Phase 1 dose-escalation it is suggested that at least 3 subjects with MLLr or NPM1m are included at each dose level that is anticipated to be clinically active, to allow for optimal evaluation of safety and efficacy in the presumed target population to guide selection of the optimal RP2D. As described in Section 3.2, we will use the same the elimination boundaries in Table 4 for the toxicity monitoring in the expansion cohort(s).

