#### **9.4.7. Safety Analyses**

Safety analyses will be performed in the safety population. AEs that occur or worsen relative to the pre-treatment state after the start of study treatment and within 30 days of the last dose of study drug (TEAEs) will be tabulated. AEs will be coded using the Medical Dictionary for Regulatory Activities (MedDRA) terminology and tabulated by body organ group using the MedDRA system organ class (SOC) and by AE term using preferred terms (PTs).

Safety evaluation will include DLTs, serious adverse events, treatment-emergent adverse events, physical examination findings (including ECOG performance status), vital signs measurements, standard clinical laboratory parameters, and ECG parameters (including QTcF).

Safety analyses in general will be descriptive and will be presented in tabular format with the appropriate summary statistics by dose level and in total for Phase 1, and by cohort and in total for Phase 2, unless otherwise stated. Only the treatment emergent assessments (i.e., assessments within the 30 days of last study drug dose) would be used in the analyses unless otherwise specified.

The summary of DLTs in the Dose Escalation parts will be performed based on the DLT Evaluable Set. All other safety summaries and analyses will be performed based on the Safety Analysis Set and subjects will be analyzed according to the actual treatment they received.

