##### **9.4.7.1. Dose-Limiting Toxicities**

For Phase 1 (Dose Escalation), the number of DLTs identified among the DLT evaluable subjects in the DLT Evaluable Set will be listed and summarized for each dose cohort and in total by the worst NCI-CTCAE grade, system organ class (SOC), and preferred term (PT).

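### The DLT Evaluable Set uses a twice-daily dose count (42 of 56), so no DLT-free once-daily subject can enter it, contrary to the 75% rule in Section 3.2.2

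*Combined protocol and SAP*

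**What the plan says.** Section 9.4.1.3 defines a single DLT Evaluable Set for the whole of dose escalation. A subject with a DLT in the first 28-day cycle enters whatever the number of doses taken. A subject without one enters only if he or she "has received at least 42 out of the 56 DS-1594b doses and has completed the DLT evaluation period". No separate figure is given for once-daily dosing.

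Section 3.2.2 has its own evaluability rule for the same 28 days: "Subjects must receive at least 75% of the doses of DS-1594b". It names no dosing frequency.

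Once-daily dosing is provided for in detail. Section 3.1 allows a switch to QD, or both regimens at once with alternating assignment. Section 5.1.1 states that "BID and QD cohorts can be enrolled in parallel and will be evaluated independently for DLT". Section 5.1.2 specifies that "for QD dosing, subjects should take DS-1594b tablets once daily". Table 15 gives a full QD sampling schedule.

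The set is used in Section 9.4.7: "The summary of DLTs in the Dose Escalation parts will be performed based on the DLT Evaluable Set". Section 9.4.7.1 adds that DLTs among "DLT evaluable subjects in the DLT Evaluable Set will be listed and summarized for each dose cohort and in total".

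The expression DLT evaluable also appears in the dose-finding text. Section 9.1 has the BOIN evaluation made "separately based on the cumulative number of DLT evaluable subjects treated in that dose level", and Section 3.2 does the same by regimen. Section 6.9 requires at least 3 such subjects before a subject may be escalated to a dose level or switched to the other regimen.

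**The concern.** The SAP threshold appears to have been written for BID dosing and not revised when QD was added. For a QD subject it cannot be reached, so membership of the set depends on having had the event that the set is meant to count. A fully compliant, DLT-free QD subject is evaluable under Section 3.2.2 and excluded under Section 9.4.1.3.

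At stake is the Phase 1 DLT summary, which supports a primary safety objective. A DLT count can be interpreted only against the number evaluable, and that number is what fails. A second question is which definition applies where Sections 3.2, 6.9 and 9.1 speak of DLT evaluable subjects, since none of them gives a cross-reference for the term.

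**Working it through.** **Inputs.** DLT window: 28 days (Section 3.2). Doses per day: 2 for BID, 1 for QD (Section 5.1.2). Evaluability fraction: 75% (Section 3.2.2). SAP threshold: 42 of 56 (Section 9.4.1.3). Elimination boundary at 3 subjects: 2 DLTs (Table 4).

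**Reproducing the SAP figure.** Planned doses = 28 × doses per day; threshold = 0.75 × planned doses.

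| Regimen | Planned doses | 75% of planned | 42 ÷ planned |
|---|---|---|---|
| BID | 28 × 2 = 56 | 42 | 0.75 |
| QD | 28 × 1 = 28 | 21 | 1.50 |

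For BID the two sections agree exactly. For QD, 42 doses is 150% of the most that can be taken, so no DLT-free subject qualifies.

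**QD dose cohorts, assuming full compliance.** Under Section 3.2.2 all treated subjects count. Under Section 9.4.1.3 only those with a DLT do.

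| QD subjects | DLTs | Section 3.2.2 | Section 9.4.1.3 |
|---|---|---|---|
| 3 | 0 | 0/3 | empty set |
| 6 | 1 | 1/6 = 16.7% | 1/1 |
| 9 | 2 | 2/9 = 22.2% | 2/2 |

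**How readily the set is empty.** For a fixed number n of QD subjects and a true DLT rate p, P(no DLT) = (1 − p)^n. For n = 3 this is 0.80³ = 51.2% at p = 0.20 (the target rate) and 0.90³ = 72.9% at p = 0.10.

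**Pooled total.** Take 9 BID subjects with 1 DLT and 6 QD subjects with 1 DLT. Section 3.2.2 gives (1 + 1)/(9 + 6) = 2/15 = 13.3%. Section 9.4.1.3 gives (1 + 1)/(9 + 1) = 2/10 = 20.0%.

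**Only if the SAP definition also governed Section 6.9.** Three DLT evaluable QD subjects would be three subjects with a DLT. Table 4 eliminates a dose at 2 of 3, so no QD level could meet the Section 6.9 condition.

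**The case against.** The arithmetic is not in dispute. The case on the other side concerns reach and size.

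- **Dose finding probably follows Section 3.2.2.** Section 9.1 refers to Section 3.2 for the details of the BOIN design, Section 3.2 refers to 3.2.2 for DLTs, and 3.2.2 states who is evaluable. The named set is used only for reporting. This is the more natural reading, and on it BOIN decisions, MTD selection and the Section 6.9 condition are unaffected. It is nevertheless inferred: no sentence gives precedence, and Section 9.4.7.1 joins the general term to the named set.
- **The counts survive.** Section 9.4.7.1 asks for the number of DLTs and does not promise percentages, unlike the adverse-event summaries in Section 9.4.7.2.1. This stands. The error lies in any denominator shown, and one is likely, because Section 9.4.7 calls for appropriate summary statistics.
- **The empty-set figures are not design probabilities.** They fix n, whereas under Table 4 a level with 0 DLTs in 3 subjects triggers escalation. This also stands, so only n = 3 is given here, as an illustration.
- **QD is optional and the intent is plain.** Both are true. Section 8.4 shows a similar leftover, with the dosing interval fixed at 12 hours. But recovering the intent means departing from the SAP's written definition, possibly after DLT data have been seen.

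**Conclusion.** The concern holds. Section 9.4.1.3 contradicts Section 3.2.2 for QD subjects, and no other section supplies a QD threshold for the analysis set. Followed as written, the DLT summary would take in QD subjects only if they had a DLT. Any QD denominator would equal the number of subjects with a DLT, and a pooled total would be inflated, as in the example where 13.3% becomes 20.0%.

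The limits are clear. BID subjects are unaffected, no DLT is lost, and nothing changes if no QD cohort opens. The illustrations assume full compliance and invented cohort sizes. An effect on dose decisions or on the Section 6.9 condition requires reading the SAP definition into those sections, which the text does not rule out but does not favour. This should be fixed before a QD cohort is analysed; it does not call the design into question.

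**What to change.** In Section 9.4.1.3, replace the fixed dose count with the protocol's own fraction: a DLT-free subject must have completed the DLT period and taken 75% or more of the DS-1594b doses planned for the assigned regimen in the first 28 days (42 of 56 for BID, 21 of 28 for QD). Add a cross-reference to Section 3.2.2, and state that this single definition applies wherever DLT evaluable is used in dose escalation: Sections 3.2, 6.9, 9.1 and 9.4.7.1.

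The cost is one sentence and a cross-reference. Sample size, trial conduct and data collection do not change, and no dosing rule is altered.
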